6.2.3 Sensitivity analyses

If the first co-primary endpoint (reduction in ABSS) is not normally distributed, we will run sensitivity analyses using negative-binomial regression (if data are positively skewed) or other transformations (i.e., square root transformation for positively-skewed data or square for negativelyskewed data).

6.2.4 Subgroup analyses

We will perform stratified analyses on the two primary endpoints for:

- Sex (men and women)
- Type of site (PCPs and walk-in clinics)
- Smoking status

While COVID-19 was a pre-planned analysis in the protocol, it is no longer possible since there is no testing for SARS-CoV-2 infection.

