2.3 Sample size

The sample size was calculated for each of the co-primary outcomes, using a Bonferroni correction for the significance level (.05 / 2 = .025). It was replicated in Stata 18 as follows:

- Reduction of symptom severity: Using a two-sample means test with power = 80%, a two-sided significance level = 2.5%, an allocation ratio 1:1, one day of difference between groups (Δ=1), and a standard deviation of 3 days assumed to be the same in both groups (1), we needed n=346 (173 in each group).
- Antibiotics use: Using a two-sample proportions test (Pearson's chi-squared test) with power = 80%, a two-sided significance level = 2.5%, an allocation ratio 1:1, a proportion of 60% in the control group and 45% in the intervention group (Δ =15) (2), we needed n=420 (210 in each group).

The largest sample size estimation was selected: n=420. As this approach is rather conservative (e.g., it does not consider the fact that the co-primary outcomes may be correlated), we did not account for potential drop-out in the sample size calculation.

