4.1 Confidence intervals and *P* values

Statistical tests will be two-sided with a 5% significance level, except for the co-primary outcomes, for which a 2.5% significance level is used. We will present 95% confidence intervals, used to assess the precision of the estimates. We will not calculate p-values for baseline comparisons.

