5.3 Baseline patient characteristics

Baseline parameters will be presented as means and standard deviations for continuous variables, or percentages and n for categorical variables.

The baseline table will include standardized mean/proportion differences to have an overview of the balance between groups, but no p-values or confidence intervals.

Relevant baseline covariates include:

- Socio-demographics: sex, age, level of education (primary, secondary, or university)
- Risk factors: smoking (yes/no), comorbidities (hypertension, diabetes, cardiovascular disease, cancer, obesity),
- Illness-related variables: number of days since the beginning of symptoms, baseline ABSS, medications already used (cough suppressant, expectorant, anti-inflammatory, febrifuge, other)
- Medical background: COVID-19 vaccination.

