6.2 Analysis methods

6.2.1 Primary analysis

The primary analysis will be done according to the FAS (ITT) and PP sets specified in section 4.2, using the adjusted model (4, 5). The randomization group will be used as the main predictor, adjusting for the stratification factors and relevant predefined covariates. To account for the fact that participants are clustered in PCP practices, we will use bootstrapped standard errors (1000 reps). A random seed will be predefined for replicability. The intraclass coefficient is expected to be small. All effects will be shown using marginal point estimates (accounting for adjustment variables) and 95% confidence intervals.

For the first co-primary endpoint, reduction in ABSS, we will use a linear regression, e.g.:

bootstrap, reps(1000) seed(XXX): regress y x1 x2

This endpoint should be normally distributed, as observed in previous studies (3). However, if it is not normally distributed, we will use a log-transformation after adding the constant 1.

For the second co-primary endpoint, *proportion of antibiotics use*, we will use a logistic regression, e.g.:

bootstrap, reps(1000) seed(xxx): glm y x1 x2, fam(bin) link(log) eform

We will use multiple imputation to handle missing values on covariates and outcomes (see section 6.4). If there is collinearity between covariates, we will remove one collinear variable based on theoretical reasons.

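### Subgroups are analysed by stratification only, with no interaction test, so the plan gives no valid way to assess whether the treatment effect differs between them

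*Combined protocol and SAP*

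**What the plan says.** Section 6.2.4 is the only text on subgroup methods. It reads "We will perform stratified analyses on the two primary endpoints for" three factors: sex, type of site (PCP practice or walk-in clinic) and smoking status, which section 5.3 records as yes or no. It names no model, no interaction term and no way of comparing the strata.

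Section 6.2.1 describes the main model: "The randomization group will be used as the main predictor, adjusting for the stratification factors and relevant predefined covariates". Treatment enters as a main effect, and both example commands are main-effects models. The same section says that effects will be shown as marginal estimates with 95% confidence intervals.

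On significance levels, section 4.1 says: "Statistical tests will be two-sided with a 5% significance level, except for the co-primary outcomes, for which a 2.5% significance level is used". It does not say which level applies to subgroup analyses of the co-primary outcomes.

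**The concern.** A subgroup analysis is meant to show whether the treatment effect depends on a patient or site characteristic. An estimate within each stratum does not answer that. The answer lies in the difference between the two stratum effects and its standard error, which is what an arm-by-subgroup interaction estimates from the whole sample.

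Three two-level factors and two endpoints give twelve within-stratum results and no measure of any difference between them. A reader is then likely to compare significance, and could conclude that Kaloba works in one sex or one type of site only. With about 40 PCPs and 5 walk-in clinics (section 2.1), the site-type strata may also be unequal in size, and discordant significance is most likely when strata are unequal.

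**Working it through.** **Inputs.** From section 2.3: a difference of 1 day with SD 3 days for the symptom endpoint; 60% against 45% for antibiotics; 80% power; two-sided 2.5%; N = 420 (210 per group). From section 4.1: 5% in general and 2.5% for the co-primary outcomes, so both are run. Subgroup shares are not in the documents; the smaller share is assumed and varied from 10% to 50%.

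**1. Reproducing the sample size.**
- Symptom endpoint: 2 × 3² × (2.241 + 0.842)² / 1² = 18 × 9.505 = 171.1, so 172 per group by the normal approximation and 173 by the noncentral t. This matches the SAP's 346.
- Antibiotics: [2.241 × √(2 × 0.525 × 0.475) + 0.842 × √(0.60 × 0.40 + 0.45 × 0.55)]² / 0.15² = 209.4, so 210 per group. This matches 420.
- At 210 per group and the 2.5% level, power is 80% for antibiotics and 88% for the symptom endpoint, so the two endpoints need separate figures.

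**2. Discordant significance under a uniform planned effect.** With n = 210 × share per arm and z = 1.960 or 2.241:
- Symptom power = Φ(1 / (3√(2/n)) − z)
- Antibiotics power = Φ((0.15√n − 0.706z) / 0.698)
- P(exactly one subgroup significant) = p1(1 − p2) + p2(1 − p1)

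At 50:50, n = 105. Symptom power is Φ(2.415 − 1.960) = 0.676 at 5%, and discordance is 2 × 0.676 × 0.324 = 43.8%. Antibiotics power is 0.474 at 2.5%, and discordance is 2 × 0.474 × 0.526 = 49.9%. All results in per cent:

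| Split | Antibiotics, 5% | Antibiotics, 2.5% | Symptom, 5% | Symptom, 2.5% |
|---|---|---|---|---|
| 50:50 | 48.5 | 49.9 | 43.8 | 49.0 |
| 40:60 | 50.2 | 51.3 | 46.0 | 51.0 |
| 30:70 | 55.1 | 55.6 | 52.2 | 56.7 |
| 20:80 | 62.8 | 62.2 | 62.2 | 65.3 |
| 10:90 | 72.8 | 70.3 | 74.8 | 75.7 |

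**3. No treatment effect.** Discordance is 2α(1 − α): 2 × 0.05 × 0.95 = 9.5% per factor at 5%, and 2 × 0.025 × 0.975 = 4.9% at 2.5%.

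**4. The interaction test in the same setting.** In 8,000 simulated trials of the symptom endpoint with a uniform 1-day effect and assumed smaller shares of 50%, 20% and 30%, the interaction test gave a false signal in 4.6-5.0% of trials per factor at the 5% level and 2.5-2.6% at the 2.5% level. In the same trials, at least one of the three factors showed discordant significance in 82% (5% level) or 84% (2.5% level).

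**5. Power of the interaction test at 50:50.**
- Symptom, 1-day difference in effect: SE = 3√(4/105) = 0.586 and 1/0.586 = 1.708, so power is 40% at the 5% level and 30% at 2.5%.
- Antibiotics, 15-point difference in effect (risk-difference scale): SE = √(2 × 0.4875/105) = 0.0964 and 0.15/0.0964 = 1.557, so power is 34% at the 5% level and 25% at 2.5%.

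**6. Three interaction tests per endpoint.** If independent, the chance of at least one false signal is 1 − 0.95³ = 14% at the 5% level, or 1 − 0.975³ = 7% at 2.5%. The simulation gave 13.9% and 7.3%.

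**The case against.** The strongest reply is that the SAP nowhere says subgroups will be compared by their separate p-values. Section 6.2.4 mentions no p-values, and section 6.2.1 promises estimates with confidence intervals. A reader might infer that the plan prescribes the significance comparison; the documents do not support that. The defect is a missing test and a missing rule of interpretation. Reporting intervals does not remove the risk, because a 95% interval that excludes the null is a significant result at 5%.

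A reader might also infer that stratified analyses produce false differences about half the time whatever the truth. That is too strong. The high figures need a uniform true effect near the planned size and readers who compare significance; with no effect the figure falls to about 5-10% per factor.

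A third tempting figure is the chance of at least one significant result among the six within-stratum tests of one endpoint when treatment does nothing: 1 − 0.95⁶ = 26%, or 1 − 0.975⁶ = 14%. That describes multiplicity, not false heterogeneity, and it assumes independence although the three factors divide the same patients. It should not be cited for this point.

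Two further replies stand. Subgroup effects are not among the objectives in section 1.2, so the primary conclusions do not depend on them. And an interaction test has limited power here.

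**Conclusion.** The point holds as a gap in method. The plan has within-subgroup analyses and nothing that tests or estimates a difference in effect between subgroups. The 44-50% (50:50) and 52-57% (30:70) figures rest on a uniform effect of the planned size, assumed subgroup shares, and unadjusted calculations that ignore clustering by PCP, dropout and imputation. Over the whole assumed range of 10% to 50% for the smaller subgroup, discordance stays between 44% and 76%, far above the nominal 5% or 2.5% of an interaction test. The change should be made; its importance is limited to the subgroup claims in the report.

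**What to change.** For each of the three factors, add an arm-by-subgroup interaction term to the section 6.2.1 FAS model for each co-primary endpoint. Use the mean-difference scale for the symptom endpoint and the risk-ratio scale of the log-link model for antibiotics. Sex, smoking status and type of recruitment are already in the full adjustment set under E1.1 and E2.1, so each model gains one product term.

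Report the interaction estimate with its 95% CI and p-value beside the subgroup estimates and their 95% CIs. State that any claim of a subgroup difference will rest on the interaction and not on within-subgroup significance. State the significance level that applies, and label the analyses exploratory.

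The cost is SAP wording and a small change to code that section 6.8 already submits to independent checking. The downside is low power: a non-significant interaction must not be reported as evidence of a uniform effect. Nor does the fix remove multiplicity, since three tests per endpoint still carry about a 14% chance of at least one false signal at the 5% level.

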6.2.5 Additional analyses

In addition, we will explore:

Time to clinical improvement: We will test how long it takes to achieve symptom recovery using a Cox regression with the randomization group predicting time to complete resolution of symptoms (adjusted model with multiple imputation, as described in section 6.2.2).

Change in ABSS: We will test the trajectory of ABSS over time. In a first step, we will calculate a group-based trajectory model (GBTM) to identify trajectories of symptom severity over time, coding the score to 0 when symptom recovery is achieved. GBTM is kind of finite mixture modelling that identifies groups of individuals who share a similar trajectory based on a multinomial strategy with maximum likelihood estimation (9). The number of trajectories will be selected using usual fit indices: Akaike Information Criterion (AIC), Bayesian information criterion (BIC), loglikelihood, entropy, and the percentage of participants in each class ($\geq 5\%\%$). We will then test whether the group membership is associated with the randomization group using a multinomial regression with bootstrapped standard errors, adjusting for covariates. Odds-ratios will be reported.

Time to antibiotics use: We will test how long it takes to use antibiotics using a Cox regression, with the randomization group predicting time to antibiotics use (adjusted model with multiple imputation, as described in section 6.2.2).

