6.1 Outcome definitions

Reduction of symptom severity. The first co-primary endpoint uses the patient-reported outcome Acute Bronchitis Severity Score (ABSS), which quantifies the severity of 5 symptoms related to acute bronchitis for the previous 24 hours. It is assessed on a scale from 0 to 4, with the sum score ranging between 0 and 20 (see Table 1) (3). Participants will complete the ABSS daily on an online diary, until symptom resolution and up to 21 days. If the participant does not answer, the ABSS will be evaluated in phone interviews (days 4, 8, and 22).

Symptom	0	1	2	3	4
Overall severity of illness	Very mild	Mild	Moderate	Serious	Very serious
Day cough	1-2 times/day	3-5 times/day	6-10 times/day	11-20 times/day	>20 times/day
Night cough	1-2 times/night	3-5 times/night	6-10 times/night	11-20 times/night	>20 times/night
Limit daily activity	None	Mild	Moderate	Severe	Very severe
Subjective fever	None	Mild	Moderate	Severe	Very severe

Table 1. Acute Bronchitis Severity Score (ABSS)

The first co-primary is the number of days needed to achieve a 50% reduction in the ABSS after peak of symptoms (1). The peak of symptoms is defined as the highest ABSS observed during the study.

The procedure to calculate the first co-primary endpoint is the following:

- Calculate daily ABSS (sum score of the 5 symptoms)
- Calculate the peak (max. ABSS observed)
- Calculate daily percentage change in the ABSS after the peak
- Calculate which day corresponds to a 50% decrease
- Calculate the number of days between the peak and the 50% decrease

If there is no peak, the first day will be used as the peak. If the 50% decrease is not reached, we will set the number of days to the maximum (22 days). Imputation will be used for missing values on daily ABSS (see section 6.4). We will run a sensitivity analysis computing the primary outcome and using multiple imputation on the primary outcome.

Antibiotics use. The second co-primary endpoint is the proportion of participants who take antibiotics after the initial visit (\geq day 2). It is defined as 0=no antibiotics during the same illness episode and 1=antibiotics use during the same illness period. Antibiotics use is assessed daily in the diary (day 1 to 21) until symptom resolution and at the three phone calls at day 4, 8, and 22.

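### The ABSS trajectory analysis regresses class membership on arm with no allowance for classification error, so arm effects will generally be understated when the classes overlap

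*Combined protocol and SAP*

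**What the plan says.** SAP section 6.2.5 (Additional analyses, Change in ABSS) sets out two steps.

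- Step one: "In a first step, we will calculate a group-based trajectory model (GBTM) to identify trajectories of symptom severity over time". Arm is not named as a predictor of class here. The number of classes is chosen on AIC, BIC and log-likelihood, together with "entropy, and the percentage of participants in each class". The only numerical threshold is a class share of at least 5%.
- Step two: "We will then test whether the group membership is associated with the randomization group using a multinomial regression with bootstrapped standard errors", with covariate adjustment. "Odds-ratios will be reported".

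The section does not say how a participant is given a class (most probable class, posterior weighting or random draws). It does not say whether the bootstrap refits the trajectory model. Section 6.2.1 gives the bootstrap a different purpose: "To account for the fact that participants are clustered in PCP practices, we will use bootstrapped standard errors (1000 reps". Its example command, "bootstrap, reps(1000) seed(XXX): regress y x1 x2", resamples around the regression alone.

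The data are the diary scores described in section 6.1: "Participants will complete the ABSS daily on an online diary, until symptom resolution and up to 21 days". Section 6.2.5 introduces its analyses with "In addition, we will explore".

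**The concern.** Trajectory class is not observed. It is inferred from a noisy series of scores, and some participants will be put in the wrong class. If step two takes the assigned class as the outcome, misclassification unrelated to arm mixes the classes within each arm and generally shrinks the contrast between arms. An interval from that regression also carries no uncertainty about who belongs where.

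A GBTM is itself a finite mixture with a multinomial model for membership, so the arm effect can be estimated inside it.

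At stake is the one planned analysis that models the whole daily ABSS course by arm. It could report too small an effect and have less power to detect one. Nothing in the selection rules prevents a poorly separated solution from being chosen.

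**Working it through.** **Inputs from the SAP.** 420 participants, 210 per arm (sections 2.2 and 2.3); up to 21 daily scores (section 6.1); 5% two-sided level outside the co-primaries (section 4.1). The SAP gives no figure for the trajectory analysis, so the check starts from its sample size.

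**Step 1: the plan's own number.** For 60% vs 45%, α = 0.025 and power 80%, the mean proportion is 0.525:

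n per arm = [2.2414·√(2·0.525·0.475) + 0.8416·√(0.60·0.40 + 0.45·0.55)]² / 0.15² = (1.583 + 0.588)² / 0.0225 ≈ 209.4, so 210 per arm and 420 in total. This agrees with section 2.3.

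**Step 2: two classes, closed form.** Assumptions, not from the SAP: 40% of controls in a slow-recovery class, true OR 0.50, and the same classification accuracy *a* in both classes and arms. The treated odds are (0.40/0.60)·0.50 = 0.333, so the treated proportion is 0.25. The observed proportion is q = p·a + (1 − p)(1 − a).

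| Accuracy | q control | q treated | Observed OR | Power at 210 per arm, α = 0.05 |
|---|---|---|---|---|
| 100% | 0.400 | 0.250 | 0.50 | 91% |
| 99% | 0.402 | 0.255 | 0.51 | 90% |
| 95% | 0.410 | 0.275 | 0.55 | 83% |
| 90% | 0.420 | 0.300 | 0.59 | 73% |
| 85% | 0.430 | 0.325 | 0.64 | 60% |
| 80% | 0.440 | 0.350 | 0.69 | 47% |

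At 90%, for example: (0.30/0.70) / (0.42/0.58) = 0.59.

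**Step 3: three classes, closed form.** Assumed true ORs are 1.00 (class 2 vs 1) and 0.50 (class 3 vs 1). Ten per cent of each class is misassigned to neighbouring classes, split equally for the middle class.

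- Control shares 0.40/0.35/0.25 give treated shares 0.457/0.400/0.143. Observed shares are 0.3775/0.3800/0.2425 (control) and 0.4314/0.4200/0.1486 (treated). Observed ORs: 0.97 and 0.54.
- Control shares 0.50/0.10/0.40 give treated shares 0.625/0.125/0.250. Observed shares are 0.455/0.180/0.365 and 0.569/0.200/0.231. Observed ORs: 0.89 and 0.51.

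The real contrast moves towards 1. The null contrast moves away from it.

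**Step 4: simulation.** n = 420, 21 daily scores, two classes, a cubic Gaussian GBTM fitted by EM, 300 data sets per setting, true OR 0.50. The decay curves and residual SDs are assumed. Two-step means most probable class, then the log OR with its usual standard error, which stands in for a bootstrap around the regression alone. One-step has arm in the membership part. Covariates and PCP clustering were not simulated.

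| Entropy | Accuracy | Two-step OR | SE reported / empirical | Two-step 95% coverage | One-step OR | One-step empirical SE |
|---|---|---|---|---|---|---|
| 0.98 | 99.4% | 0.51 | 0.21 / 0.22 | 94% | 0.50 | 0.23 |
| 0.89 | 96.9% | 0.52 | 0.21 / 0.22 | 95% | 0.50 | 0.23 |
| 0.76 | 93.0% | 0.55 | 0.21 / 0.22 | 92% | 0.49 | 0.26 |
| 0.54 | 85.1% | 0.61 | 0.22 / 0.23 | 82% | 0.49 | 0.32 |

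With a true OR of 1, the two-step OR stayed at 1.00 and coverage was 95% to 98%.

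A separate three-class simulation (true OR 2.0, about 2.05 in the samples, 50 data sets per setting) gave 1.96 two-step and 2.02 one-step at entropy 0.97, and 1.68 and 2.03 at entropy 0.70.

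**Step 5: a misspecified trajectory model.** In the three-class simulation with peaks varying within class, entropy was 0.93, yet the ORs were 1.58 two-step and 1.67 one-step against a true 2.0. In the two-class setting, with participants' score levels varying within class (SD 2), entropy was 0.94 but the two-step OR was 0.86, where the true classes gave 0.495. High entropy therefore reassures only if the trajectory model fits.

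**The case against.** The strongest reply is that the SAP is silent rather than wrong. A reader might infer that it prescribes hard assignment and a bootstrap confined to the regression. It states neither; both are readings of the two-step wording and of example code written for other endpoints. That is conceded, and the point is put conditionally. The SAP would need to state the method in either case.

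A reader might also infer that every odds ratio is pulled towards 1. That is assured only for two classes with error unrelated to arm. A multinomial model suggests three or more classes, and step 3 shows a null contrast moving from 1.00 to 0.97 or 0.89.

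The claim about precision needs care too. The two-step standard error is close to that estimator's own variability, so the loss of coverage comes mainly from bias. What stands is that the two-step interval omits class uncertainty: 0.22 against 0.32 for the one-step estimator at entropy 0.54.

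Finally, up to 21 scores per person, set to 0 after recovery, may separate the classes well, and the problem would then be negligible under a well-fitting model. This is fair, but separation cannot be known in advance and no minimum is set. Other planned analyses also use the ABSS course or recovery (the first co-primary and the Cox model for symptom resolution), so this is not the only view of recovery by arm.

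**Conclusion.** The concern holds as a conditional point about an exploratory analysis, and acting on it is a cheap improvement. If assigned class is treated as observed, true arm effects on class membership will generally be attenuated and the intervals will omit class uncertainty. The effect is negligible at entropy of about 0.9 or above, provided the trajectory model is correctly specified. It is material at about 0.75 or below: a true OR of 0.50 became 0.55 at entropy 0.76 and 0.61 at 0.54. These sizes rest on assumed curves, residual SDs, class shares and arm effect, and on classification error that does not depend on arm given true class.

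A reader might go on to infer that the test of association is invalid or that the trial's main conclusions are at risk. Neither follows. In the two-class check the test under no effect was not inflated, and no co-primary result depends on this analysis.

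**What to change.** In SAP section 6.2.5:

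1. Choose the number of classes without arm, as planned.
2. Refit that model with arm and the covariates in the class-membership part and report those odds ratios, or use a bias-corrected three-step method.
3. Bootstrap the whole procedure, resampling by PCP, with class labels aligned across resamples.
4. Report entropy and mean posterior probability per class.
5. Use assigned classes for description only.

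The cost is SAP wording, one extra model fit and a longer bootstrap. Class curves can shift slightly when covariates enter the model, so both sets should be shown. The change does not remove bias from a misspecified trajectory model, so the fit of the curves within class still has to be examined.
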